## **8.4 Adverse Events, Serious Adverse Events and Unanticipated Problems**

The definitions of AEs, SAEs and UPs can be found in Appendix 1.

Adverse events will be reported by the participant's parent/caregiver.

The Investigator and any qualified designees are responsible for detecting, documenting, and reporting events that meet the definition of an AE, SAE or UP and remain responsible for following up on AEs that are serious, considered related to the study treatment or the study, or that caused the participant to discontinue the study and/or study treatment (see Section 7).

### **8.4.1 Time Period and Frequency for Collecting AE, SAE and UP Information**

All AEs, SAEs and UPs will be collected from the signing of informed consent form (ICF) until Visit 3/EOS at the timepoints specified in the SoA (Section 1.3).

All SAEs will be recorded and reported to the DSMB within 24 hours, as indicated in Appendix 1. The Investigator will submit any updated SAE data to the DSMB within 24 hours of it being available.

Investigators are not obligated to actively seek AEs, SAEs or UPs after the conclusion of study participation. However, if the Investigator learns of any UP or SAE, including a death, at any time after a participant has been discharged from the study, and he/she considers the event to be reasonably related to the study treatment or study participation, the Investigator must promptly notify the DSMB.

The method of recording, evaluating, and assessing causality of AEs, SAEs and UPs and the procedures for completing and transmitting SAE and UP reports are provided in Appendix 1.

### **8.4.2 Method of Detecting AEs, SAEs and UPs**

Care will be taken not to introduce bias when detecting AEs and/or SAEs. Open-ended and non-leading verbal questioning of the participant is the preferred method to inquire about AE or UP occurrence. The only exception to this is the specific monitoring for risk of suicidal ideation

(as described in section 8.2.3), potential liver toxicity (as described in section 8.2.2) and specific monitoring for reactive airway disease.

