### **8.3 Safety Assessments**

- Planned time points for all safety assessments are provided in the SoA.
- Safety monitoring will be guided by the established safety profiles of atomoxetine and oxybutynin, and by Phase 1 safety data for the combination. Safety assessments will include measurement of vital signs, monitoring and recording of AEs, SAEs, suicidality assessment, recording of study or treatment discontinuations. Effects on OSA and sleep parameters (e.g., sleep time and sleep stages) will also be monitored by PSG.
- Adverse events of special interest include effects on urine outflow, as both atomoxetine and oxybutynin are associated with urinary retention. Effects of atomoxetine on heart rate and blood pressure are expected to be modest, as indicated by the initial data described above, and will also be monitored. Participants with congenital heart disease will require clearance from their cardiologist in order to participate in the study. Suicidal ideation in children and adolescents is a boxed warning for atomoxetine. Therefore, safety monitoring in the dose-finding study will use an appropriate questionnaire to monitor for the potential emergence of suicidal ideation or depression. We will also specifically monitor for symptoms of reactive airway disease during safety monitoring. This will include questions related to wheezing as well as use of bronchodilator medications.

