### 8.3.2 Clinical Safety Laboratory Assessments

- To minimize discomfort to the child participants of the study, no routine blood draws will be included as part of the study. Both study agents are FDA-approved and do not require any laboratory monitoring.
- A urine pregnancy test will be performed on all female participants age 10 and older prior to study randomization.
- There are case reports of liver toxicity associated with atomoxetine, however large scale studies have not shown any increased risk of liver toxicity. There were no cases of liver-related SAEs during all clinical trials of atomoxetine in children and adults, which included 7,691 participants. Additionally, there are only three reports of liver toxicity related to atomoxetine in post-marketing surveillance of atomoxetine (with >10 years of monitoring), which all resolved with drug discontinuation. Therefore, to minimize risk of harm to participants, we will specifically inquire about evidence of jaundice or skin color changes during weekly phone calls while on study drugs but will not require blood draws for all participants. Participants that are found to have jaundice will have study drug discontinued and be referred for further medical management. These participants will be monitored until their condition stabilizes or resolves.

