### 8.3.3 Suicide Risk Monitoring

Suicidal ideation in children and adolescents is a boxed warning for atomoxetine. However, post-marketing safety data has not shown an increased risk of suicidality associated with atomoxetine use (Bangs, Wietecha et al. 2014, Reed, Buitelaar et al. 2016). Additionally, suicidality appears uncommon in individuals with DS, regardless of atomoxetine use. There are no reports of suicide or suicidal ideation occurring in any children or adolescents with Down syndrome (DS), and a total of three reported suicide attempts in older individuals with DS (none associated with atomoxetine). Given this, the likelihood of suicidal ideation appears very low for this study. To further reduce the risk of suicide, we have excluded participants with current depression. Given the paucity of literature on suicidal ideation in DS, there are no available screening tools available for suicidality in DS. Therefore, we will instead monitor mood using the depression subscale of the Anxiety, Depression and Mood Scale (ADAMS), a screening tool for individuals with cognitive impairment which has been validated in a sample that included children with DS. In addition, we will use a single screening question from the Child Behavior Checklist (a validated behavior questionnaire for age 6-18) for suicidality: “Does your child talk about killing themselves?” For subjects that answer positively (somewhat true or often true), they will be flagged for immediate detailed assessment by the study PI, and appropriate actions will be taken,

including discontinuation of study medication as well as referral to behavioral health emergency services if indicated. This screening will occur weekly while subjects are on study medications. If this occurs, participants would be monitored until their suicidal ideation resolves.

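### Urine outflow is named an adverse event of special interest, but the protocol states no directed question or measurement for it

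*Combined protocol and SAP*

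**What the plan says.** Section 8.3 identifies the risk and gives the reason: "Adverse events of special interest include effects on urine outflow, as both atomoxetine and oxybutynin are associated with urinary retention". It goes on to say that heart rate and blood pressure will be monitored too, which implies that urine outflow is monitored, but it gives no method.

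Section 8.4.2 sets the general method of detection. It opens with "Care will be taken not to introduce bias when detecting AEs and/or SAEs" and continues: "Open-ended and non-leading verbal questioning of the participant is the preferred method to inquire about AE or UP occurrence". It then limits the departures: "The only exception to this is the specific monitoring for risk of suicidal ideation", together with potential liver toxicity "and specific monitoring for reactive airway disease". No urinary item appears.

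Elsewhere, urinary retention is an exclusion at entry (5.2), anticholinergic drugs are disallowed (6.5), and acute urinary obstruction is an individual stopping criterion (7.2.1). The Schedule of Activities (1.3) has one generic row for adverse event screening. Section 8.4 makes the parent or caregiver the reporter of adverse events.

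**The concern.** The protocol singles out a risk shared by both drugs, then assigns it by omission to the general method from which three other risks are exempted. Every child takes both drugs in both four-week periods, so the exposure is present throughout treatment.

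The main stake is participant safety. The named urinary stopping criterion is acute obstruction, which is the late stage. Hesitancy, straining or reduced voiding could be judged under the 7.2.1 rule for any other adverse event, but only after someone reports it. Participants are children aged 6 to 17 with Down syndrome, and 8.4.2 directs its questioning at the participant, so report of such symptoms without a specific question may be limited. A lesser stake is the completeness of the descriptive counts for an event named in advance.

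**Working it through.** The protocol gives no figure to reproduce. The check is a comparison of sections and a count of contacts.

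**Step 1. How each named risk is to be detected**

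| Risk | Listed exception in 8.4.2 | Stated content or measurement |
|---|---|---|
| Suicidal ideation | Yes | One worded question from a validated checklist plus a depression subscale, weekly on drug (8.3.3) |
| Liver toxicity | Yes | Weekly telephone inquiry about jaundice or skin colour (8.3.2) |
| Reactive airway disease | Yes | Wheezing and bronchodilator use (8.3) |
| Heart rate and blood pressure | Not needed | Measured as vital signs (8.3.1) |
| Urine outflow | No | None stated |

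All three listed exceptions have a stated question or topic. On airway disease, for example, 8.3 says "This will include questions related to wheezing as well as use of bronchodilator medications". Urine outflow has no stated question, topic or on-treatment measurement.

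**Step 2. Whether the listed exceptions explain the omission**

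They have reasons of their own. For suicidality, 8.3.3 notes that "Suicidal ideation in children and adolescents is a boxed warning for atomoxetine". The liver inquiry stands in for laboratory monitoring: staff ask about jaundice or "skin color changes during weekly phone calls while on study drugs but will not require blood draws for all participants". These reasons justify including those risks but give none for leaving urine outflow out. The comparison does not rank the risks.

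**Step 3. Whether a urinary method appears anywhere else**

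The remaining urinary references are:
- the indication for oxybutynin (2.2.3, 4.3);
- the entry exclusion (5.2);
- the acute-obstruction stopping rule (7.2.1);
- urine pregnancy testing (5.2, 8.3.2);
- urinalysis as a generic example in the adverse event definition (10.2).

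None is a means of detecting a voiding problem during treatment.

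**Step 4. Contacts at which a question could be asked**

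The Schedule of Activities marks adverse event screening at calls 1–3, Visit 2, calls 4–6 and Visit 3.
- Per child: 3 + 1 + 3 + 1 = 8 contacts.
- All 27 randomized: 8 × 27 = 216, an upper limit.
- 24 completers: 8 × 24 = 192.

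**Step 5. Spacing of those contacts within a period**

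- Nominal: 14 − 7 = 7 days.
- Widest under the ±4-day windows: (14 + 4) − (7 − 4) = 15 days.

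These figures describe opportunities to ask, not events missed. No event rate or capture rate is assumed.

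**The case against.** The best case for the plan is that a safety net already exists. Families are asked about problems at eight contacts. Open-ended questioning is only the preferred method, so a urinary question is not forbidden, and the protocol nowhere says that an event of special interest must be actively solicited. Keeping the exceptions few serves the stated aim of avoiding detection bias. Risk is lowered by the entry exclusion, the ban on anticholinergics and an oxybutynin dose of 5 mg once nightly, against a recommended paediatric start of 5 mg twice daily (4.3). An independent monitor reviews study risks with the family and can be reached by telephone at any time (10.1.5). Call scripts and adverse event forms are not in the documents and consent pages were removed, so what families are actually told or asked is unknown.

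Much of this stands, and it limits the size of the gain. The gap is between a general and a directed question; it is not an absence of contact. The safeguards reduce risk, but they do not detect an event. The monitor's risk review takes place at the first call, before the initial sleep study and so before dosing; it may alert families, but it is not on-treatment inquiry. If unseen scripts do ask about voiding, they depart from the closed list in 8.4.2, and the amendment would bring the two into line. Any limit on what a caregiver can observe, particularly in an adolescent, applies to the proposed question as well.

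**Conclusion.** The concern holds. The protocol names urine outflow as an event of special interest, states no directed question or measurement for it, and leaves it off a list of exceptions worded as complete. Confidence in that reading is high.

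The size of the benefit is unknown, because the documents report neither how often urinary events occur nor how often they are volunteered. The expected gain is earlier notice of milder voiding problems and fuller descriptive counts. No consequence for the dose comparison is claimed. The conclusion concerns what the protocol states and does not presume what unseen operational documents contain. The change is recommended because it makes a named safety interest detectable at little cost.

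**What to change.** Add urine outflow to the exceptions in 8.4.2. Ask the caregiver one fixed question about voiding difficulty (straining, marked delay, or reduced or absent urination) at the six scheduled calls and at Visits 2 and 3, with identical wording in both blinded periods. Send any positive answer to the investigator for the judgment already provided for in 7.2.1. The same edit can correct the cross-references in 8.4.2, which cite 8.2.3 and 8.2.2 where the text is in 8.3.3 and 8.3.2.

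The cost is one question at 8 existing contacts per child, with no new visit or procedure. There are two downsides. Prompting may raise the raw count of urinary complaints, a cost the protocol already accepts for three other risks and one that should fall similarly on both blinded periods. A roughly weekly question will also not catch retention that develops quickly between contacts.

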#### **8.4.3 Follow-up of AEs and SAEs**

After the initial AE/SAE report, the Investigator is required to proactively follow each participant at subsequent visits/contacts. All SAEs will be followed until resolution, stabilization, until the event is otherwise explained, or the participant is lost to follow-up (as defined in Section 7.4). Further information on follow-up procedures is given in Appendix 1.

#### **8.4.4 Regulatory Reporting Requirements for SAEs and UPs**

- Prompt notification (within 24 hours, see Appendix 3) by the Investigator to the DSMB of an SAE is essential so that legal obligations and ethical responsibilities towards the safety of participants and the safety of a study treatment under clinical investigation are met.
- The Sponsor has a legal responsibility to notify both the local regulatory authority and other regulatory agencies about the safety of a study treatment under clinical investigation. The Sponsor will comply with country-specific regulatory requirements relating to safety reporting to the regulatory authority, IRB, and Investigator.
- Investigator safety reports must be prepared for suspected unexpected serious adverse reactions (SUSAR) according to local regulatory requirements and Sponsor policy.

#### **8.5 Treatment of Overdose**

For this study, any dose of atomoxetine greater than 80 mg and of oxybutynin greater than 5 mg more frequently than QHS will be considered an overdose.

In the event of an overdose, the Investigator should refer to the approved product label for advice on overdose and:

1. Closely monitor the participant for AE/SAE.
2. Document the quantity of the excess dose as well as the duration of the overdosing in the eCRF.

Decisions regarding dose interruptions or modifications will be made by the Investigator based on the clinical evaluation of the participant.

#### **8.6 Pharmacokinetics**

PK parameters are not evaluated in this study.

## 9 Statistical Considerations

### 9.1 Statistical Hypotheses

The null hypothesis is no difference in change from baseline in obstructive AHI in the high dose ato-oxy study period compared to the low dose ato-oxy study period.

### 9.2 Sample Size Determination

Under the mixed effects model setting the primary analysis for comparing high dose ato-oxy with low dose ato-oxy is reduced to a two-sample t test with a common variance of  $\sigma^2/2$ , where  $\sigma^2$  is the residual variance (Hills and Armitage 2004). Based on prior research with a sample size of 20 subjects, a median change of -15.9 in AHI with interquartile range (-35.9, -7.3) was observed with a p-value of <0.001 (effect size [Cohen's d] of 1.4) (Taranto-Montemurro, Messineo et al. 2018). Given this, we plan to use 24 subjects (12 per dose sequence) which will have a power of 80% to detect an effect size of 1.20 standard deviations for changes in AHI, OSA-18 total score and arousal index, respectively, based on a two-sided test with  $\alpha=0.05$ . We estimate a 10% attrition rate for the study and, therefore, will recruit a total of 27 participants.

### 9.3 Populations for Analyses

For the purposes of analysis, the following analysis sets are defined:

Population	Description
Enrolled	All participants who signed the ICF (including screening failures).
Modified Intent to Treat (mITT) Population	The mITT Population comprises all participants who are randomized, take at least 1 dose of any of the study treatments, and have at least 1 measurement on the primary endpoint. Participants will be analyzed for efficacy according to the treatment group into which they are randomized.
Safety Population	The Safety Population consists of all participants who are randomized and receive at least 1 dose of any of the study treatments. Participants will be analyzed for safety based on the treatment received.
Per Protocol (PP) Population	The PP Population consists of all participants without any major protocol violations that could influence efficacy assessment, and who are at least 80% compliant with the study medication. Participants in this population will be analyzed according to the treatment they actually received.

The primary endpoint comparison between the high dose ato-oxy and low dose ato-oxy will consider all mITT participants randomized to those 2 groups.

## 9.4 Primary and Secondary Analyses

Below is a summary of planned statistical analyses of the primary, secondary and exploratory endpoints.

For the primary outcome, each participant's changes in obstructive AHI from baseline will be derived for both periods (high dose ato-oxy and low dose ato-oxy). To account for the features of a 2 by 2 crossover design, a linear mixed effects model with a subject random effect and a dose sequence indicator (e.g. high dose ato-oxy → low dose ato-oxy sequence indicator), a period indicator (e.g. 2nd period indicator) and a high dose ato-oxy dose indicator as the covariates will be fitted to the changes in obstructive AHI. This model will allow us to evaluate the effect of high dose ato-oxy on changes in obstructive AHI compared with the effect of low dose ato-oxy (primary analysis) while accounting for the potential carry-over, period and subject effects. In addition, it will also allow us to evaluate whether the overall mean change from baseline is different from zero by testing the intercept of the model and whether the carry-over or period effect exists by testing the regression coefficient estimate for the treatment sequence indicator and the period indicator, respectively (secondary analysis). Prior research has shown that obstructive AHI is likely to be not normally distributed. Therefore, a suitable transformation will be sought and applied to changes in AHI before the mixed effects model is fitted if necessary.

For health-related quality of life aims, a similar statistical analysis plan will be implemented. Specifically, a linear mixed effects model with a subject random effect and a treatment sequence indicator (e.g. high dose ato-oxy → low dose ato-oxy sequence indicator), a period indicator (e.g. 2nd period indicator) and a high dose ato-oxy dose indicator as the covariates will be fitted to the changes in OSA-18 (secondary outcome), PedsQL and Caregiver global impression of change (exploratory outcomes), respectively. If necessary, a suitable transformation will be sought and applied to changes in these measures, although prior research has shown that OSA-18 is normally distributed (Jung, Kim et al. 2011).

For sleep architecture outcomes, we will again use a similar statistical analysis plan. Specifically, a linear mixed effects model with a subject random effect and a treatment sequence indicator (e.g. high dose ato-oxy → low dose ato-oxy sequence indicator), a period indicator (e.g. 2nd period indicator) and a high dose ato-oxy dose indicator as the covariates will be fitted to the changes in arousal index (secondary outcome) and percentage of N1, N3 and REM sleep (exploratory outcomes), respectively. For all aims, due to the cross-over design of the study, baseline covariates such as age, gender, baseline oAHI, etc. will not be included in the model as this would potentially create cross-over bias. (Kenward and Roger 2010, Mehrotra 2014).

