## 4 Study Design

### 4.1 Overall Design

This is a randomized, double blind, cross-over study of the combination of atomoxetine and oxybutynin in children with DS and OSA documented by polysomnography (PSG).

Approximately 27 participants will be randomized in the study. Participants will receive high dose ato-oxy for four weeks as well as low dose ato-oxy for four weeks in random order. During the high dose ato-oxy period, participants will take 5 mg oxybutynin and 0.5 mg/kg/day (max 40 mg) atomoxetine nightly for one week. Atomoxetine dose will then be increased to 1.2 mg/kg/day (max 80 mg) and oxybutynin will remain at 5 mg. During the low dose ato-oxy period, participants will take 5 mg oxybutynin and 0.5 mg/kg/day (max 40 mg) atomoxetine nightly. Overall study duration will be 10-15 weeks. Dosing of the study treatment will occur approximately 30 minutes prior to bedtime. Participants who withdraw from the study will not be replaced.

Study participants will undergo eligibility screening that will include an initial screening to determine whether non- PSG enrollment criteria are met, followed by a 1 night in-lab PSG and health-related quality of life assessment for participants who qualify based on non-PSG criteria. For participants who are eligible and enroll in the study, the screening PSG night will serve as the baseline measure for apnea hypopnea index (AHI) and other PSG endpoints. On the final night of dosing for both high dose ato-oxy and low dose ato-oxy, participants will return for inpatient PSG and health-related quality of life assessment. The primary efficacy endpoint is the change in obstructive AHI from baseline (high dose ato-oxy vs. low dose ato-oxy).

**Figure 2:** Overview of Study Design

Participants will be randomized to either high dose ato-oxy or low dose ato-oxy at baseline. Polysomnography (PSG) and health-related quality of life (HR-QOL) assessment will be performed after four weeks of treatment. Participants will then take no drug for two weeks, then take the alternate treatment for four weeks with repeat PSG and HR-QOL assessment at the end of therapy.

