**Exclusion Criteria based on baseline polysomnography (prior to randomization)**

1. Hypoxemia independent of respiratory events on polysomnography ( $\geq 5$  minutes with oxygen saturation <90%)

2. Presence of central sleep apnea on polysomnography (central AHI  $\geq 5$ )

3. Absence of OSA defined as total AHI <5

[figure not shown]
Children with or without history of prior adenotonsillectomy will be enrolled as long as they have current OSA (defined as AHI  $>5$ ) on baseline polysomnography. Children who are initially excluded due to tonsillar hypertrophy will be eligible to participate in the study if they have persistent OSA after adenotonsillectomy. Additionally, children will be eligible regardless of body mass index (BMI), as the prior study of ato-oxy in adults included participants with

significant obesity, and ato-oxy was demonstrated to be effective in adults with a BMI as high as 40 (Taranto-Montemurro, Messineo et al. 2018).

Pediatric OSA is defined in the International Classification of Sleep Disorders (3rd edition) by an obstructive AHI  $\geq 1$ . While we considered using this as our inclusion criteria to maximize generalizability to all children with OSA, we decided against this approach for several reasons.

First, half of our study population will be adolescents, and based on American Academy of Sleep Medicine guidance in the current polysomnography scoring manual, use of the adult definition of OSA (total AHI  $\geq 5$ ) may be more appropriate in adolescents.

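### Section 9.4 tests the overall mean change from baseline through the model intercept, which with 0/1 indicators is the low-dose, first-period mean of one sequence (about 12 children)

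*Combined protocol and SAP*

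**What the plan says.** Section 9.4 fits a linear mixed model to the changes in obstructive AHI, with a random subject effect and three fixed terms:

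- a "dose sequence indicator (e.g. high dose ato-oxy → low dose ato-oxy sequence indicator");
- "a period indicator (e.g. 2 nd period indicator");
- "a high dose ato-oxy dose indicator as the covariates will be fitted to the changes in obstructive AHI".

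As a secondary analysis, the same section says the model will be used to "evaluate whether the overall mean change from baseline is different from zero by testing the intercept of the model".

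It states no centred or sum-to-zero coding, no contrast and no least-squares mean. It excludes baseline covariates, so nothing else moves the intercept. Section 9.2 gives the planned evaluable number: "we plan to use 24 subjects (12 per dose sequence").

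**The concern.** An intercept is the expected outcome when every covariate is zero. With 0/1 indicators that is one particular combination of sequence, period and dose, not an average over the trial. The rule (test the intercept) and the named target (the overall mean change) therefore agree only under a coding that the plan does not state.

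This is the only test of change against zero that section 9.4 describes. The trial has no placebo period, so if the two doses turn out alike, readers will look to the change from baseline. A default 0/1 fit prints a line labelled intercept with a p-value. Reported under the plan's label, it would present the low-dose, first-period change in half the children as the overall result. Two analysts who both follow 9.4 could also report different results for the same named test.

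**Working it through.** **Inputs.** From 9.2: 24 evaluable children, 12 per sequence, two-sided α = 0.05, 80% power at 1.20 SD, 10% attrition. From 9.4: the three indicators, with high-to-low sequence, period 2 and high dose as the levels set to 1. The correlation rho between a child's two changes is not given, so it is varied from 0 to 1. Complete data are assumed. Standard errors are in units of the SD of a single change.

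**The plan's own figure.** A two-sample t test with 12 per sequence, an effect of 1.20 SD and 22 df has noncentral-t power of 80.2%. 24/0.9 = 26.7, rounded up to 27. Both figures reproduce.

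**What the intercept estimates.** Write E(change) = b0 + b1·sequence + b2·period + b3·dose, with 0/1 terms. The four cell means are:

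| Cell | Mean |
|---|---|
| Low-to-high, period 1 (low dose) | b0 |
| Low-to-high, period 2 (high dose) | b0 + b2 + b3 |
| High-to-low, period 1 (high dose) | b0 + b1 + b3 |
| High-to-low, period 2 (low dose) | b0 + b1 + b2 |

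Four cells and four fixed effects make the mean structure saturated, so the estimate of b0 is the first cell mean. Generalised least squares gives it weight 1, and the other three cells weight 0, at every rho tried. The average of the four cells is b0 + b1/2 + b2/2 + b3/2. With all three indicators coded −1/2, +1/2, the intercept weights each cell 0.25 and is that average.

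A REML fit to one simulated data set agreed. The 0/1 intercept was −5.025, exactly that cell's mean. The overall mean was −9.277, and so was the intercept under centred coding.

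**Wrong target (assumed effects).**

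- Low −4, high −12 events/h, no period or sequence effect: intercept −4; overall mean (−4 − 12 − 12 − 4)/4 = −8.
- The same with a period effect of +2: intercept −4; overall mean (−4 − 10 − 12 − 2)/4 = −7.
- Low 0, high −10: intercept 0; overall mean −5.

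**Precision.** SE(0/1 intercept) = sqrt(1/12) = 0.289 at every rho. SE(overall mean) = sqrt((1 + rho)/48). The ratio is 2/sqrt(1 + rho).

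| rho | SE, overall mean | Ratio | Power for the overall mean at −0.6 SD |
|---|---|---|---|
| 0 | 0.144 | 2.00 | 98% |
| 0.3 | 0.165 | 1.75 | 94% |
| 0.5 | 0.177 | 1.63 | 90% |
| 0.7 | 0.188 | 1.53 | 86% |
| 0.9 | 0.199 | 1.45 | 82% |
| 1 | 0.204 | 1.41 | 80% |

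Power for the 0/1 intercept at −0.6 SD is 51% throughout (noncentral t, 22 df for both tests, two-sided 0.05). The −0.6 SD is assumed on both doses, so both tests have the same target and only precision differs. In equivalent numbers, 24/ratio² = 6(1 + rho): the intercept test is as precise as testing the overall mean in 6 to 12 children instead of 24.

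**What does not change.** The high-dose coefficient has the same estimate and standard error under either coding (SE 0.204 at rho 0.5).

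**The case against.** - **The coding is unstated, so the plan is not definitely wrong.** The target is named in words, and centred indicators would make the sentence correct. True, and the finding is conditional on that. But indicator ordinarily means 0/1, the examples say which level is 1, and nothing in the section points to centring.
- **The sequence example is only an example.** If low-to-high were coded 1, the intercept would weight the cells +0.5 (high-to-low, period 1), +0.5 (high-to-low, period 2), +0.5 (low-to-high, period 1) and −0.5 (low-to-high, period 2). It would then use all 24 children. This limits the one-cell description to the coding in the plan's example. The intercept would still be a low-dose, period 1 value and not the overall mean: in the −4/−12 example it is again −4, and its SE is still 0.289.
- **Low values of rho are implausible because both changes subtract the same baseline.** This is reasonable. If the three PSG values had equal variances and equal correlations (an assumption), rho would be 0.5. Over rho 0.5 to 1 the SE ratio is 1.63 to 1.41 and power for the overall mean is 90% to 80%, still against 51%.
- **The 51% depends on the effect chosen.** It does. Intercept power is 38% at 0.5 SD, 75% at 0.8 SD, 85% at 0.9 SD and 91% at 1.0 SD. A large uniform effect hides the precision loss but not the wrong target.
- **No listed endpoint or hypothesis depends on this test.** Correct: the endpoints and the null hypothesis are all high versus low dose. This limits the severity. It does not make the stated test measure what it is said to measure.

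**Conclusion.** The concern holds. Under 0/1 indicators coded as in the plan's examples, the intercept test in 9.4 addresses the low-dose, first-period change in the low-to-high sequence, with 12 of 48 planned observations behind it. It does not address the overall mean change. The SE is 1.41 to 2.00 times larger than for the overall mean, and 1.41 to 1.63 times if rho is at least 0.5. The wrong target can matter more than the lost precision, by an amount that depends on how far the doses, periods and sequences differ.

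These figures rest on complete data with 12 children per sequence, an assumed range for rho and assumed effect sizes. The primary dose comparison, the period and sequence tests and the sample size are unaffected. It should be fixed, but it does not threaten the trial's main conclusion.

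**What to change.** In 9.4, replace the intercept test with the explicit contrast b0 + b1/2 + b2/2 + b3/2, or state that all three indicators are coded −1/2, +1/2. Report the least-squares mean change with 95% CI for each dose, averaged over period and sequence. Each uses all 24 children and has SE 0.204 in the units above. The intercept test is stated only for obstructive AHI; use the same contrast wherever the similar models for the other outcomes are used to test mean change.

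Two related sentences belong in the same edit:

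- The plan allows that "a suitable transformation will be sought and applied to changes in AHI before the mixed effects model is fitted if necessary". If so, test against the transformed value that corresponds to zero change, which need not be zero.
- State that these before-after changes are uncontrolled. There is no placebo, and "the screening PSG night will serve as the baseline measure for apnea hypopnea index (AHI) and other PSG endpoints". The same night decides eligibility by excluding "Absence of OSA defined as total AHI <5", so the changes may include regression to the mean.

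The cost is SAP wording only: no new data, and no change to the primary test or to the number of children.
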